**Secondary hypotheses**

The following secondary hypothesis will be tested in the study:

1. The usability of the ISC device is sufficient for participants or psychologists/psychometrists.

This will be explored with a questionnaire for participants as well as a registration by the psychologist/psychometrist of how many participants were unable to complete a test and why.

**Claims and intended performance**

The study aims to provide information that can be used to substantiate the claims listed in the table below from the regulatory plan of ISC, along with the study aim covering the claim.

Claim	Description	Covered by Study Aim
1.	A scientific model developed with KOLs that translates raw test scores to cognitive domains	4
2.	Automated scoring algorithms that give reproducible scores time after time	2
3.	Digital tests have similar psychometrics to paper test measures	1
4.	Longitudinal reporting of performance at the level of cognitive domains	3 & 4
5.	Usability by Design – high "easy to use" score for elderly users	Secondary objective
6.	Usability by Design - high user satisfaction when using digital platform	Secondary objective

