### Primary objective:

The study has four aims.

1. To compare the psychometrics of digital and paper-pencil cognitive tests. Score distributions, test-retest reliability, and construct validity of the following tests will be compared: Trail Making Test (TMT), Rey Osterrieth Complex Figure Test (ROCFT), Digit Span Test, Controlled Oral Word Association Test (COWAT), Category Fluency Test, Rey Auditory Verbal Learning Test (RAVLT), Clock Drawing Test, Star Cancellation Test, O Cancellation Test, Mini Mental Status Exam 2 (MMSE-2).
2. To assess the degree of agreement between the algorithm and manual scores for the digital Rey Osterrieth Complex Figure Test and Clock Drawing Test.
3. To estimate regression-based norms and reliable change indices.
4. To estimate factor loadings for a structural equation model describing cognition in terms of distinct cognitive domains.

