### Primary hypotheses

The following primary hypotheses will be tested in the study:

Aim 1.

- A. Digital and paper-pencil normed test scores are comparable. We consider the two versions of a test comparable when the digital normed score is on average within .3 sd of the paper normed score and the two normed scores correlate at least .6.
- B. Test-retest reliability of the digital tests is comparable to test-retest reliability of the paper-pencil tests. We consider the reliability to be comparable when we observe no significant difference in a z-test between the digital and the paper-pencil test-retest correlations.

Title: Clinical Investigation Plan		Author: [name]		Company Restricted	
DocID: ICBE-2-28674	Version: 2.0	Date: 2019-02-18	Status: Approved	Page: 20 of 35	
IRBMANAGER PILOT – QI PROJECT					

C. Construct validity of the digital tests is comparable to the construct validity of the paper-pencil tests. We consider construct validity to be comparable when confirmatory factor analysis yields the same factor structure for digital and paper-pencil tests.

Aim 2.

D. The score(s) provided by the ROCFT and Clock Drawing Test scoring algorithms on ISC are correlated highly (> .8) to the score provided by manual scoring for the same drawings.

Aims 3 & 4 have no accompanying hypotheses.

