We will use the 100 sets of digital ROCFT and Clock Drawing Test drawings, randomly drawn from the full sample, to establish agreement between scoring algorithms and manual scoring by well-trained raters (aim 2).

Title: Clinical Investigation Plan		Author: [name]		Company Restricted	
DocID: ICBE-2-28674	Version: 2.0	Date: 2019-02-18	Status: Approved	Page: 22 of 35	
IRBMANAGER PILOT – QI PROJECT					

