### 6.2 Investigational device(s) and comparator(s)

The investigational devices are the ISC product and the ISC product equivalent. The comparators are the paper-pencil tests included in the study.

Manual scores of the digital ROCFT and Clock Drawing Tests will be compared to the algorithm scores. Scoring algorithms for the ROCFT and the Clock Drawing Test are applied post-data collection. The scores estimated by the algorithms will be compared with manual scoring by a sample of well-trained raters (n = 6; aim 2). The algorithms have been developed by Philips Research and after positive comparison to the manual scores will be part of future releases of the ISC product. By comparing the manual and algorithm scoring, we can investigate the agreement between the two for the tests on the platform. This will be done by computing the relative inter-rater agreement (also known as inter-rater reliability) between the algorithm and expert raters. Relative inter-rater agreement implies that the algorithm ranks examinees the same as expert raters (n = 6).

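### Claim 2, that automated scores are reproducible, is assigned to Aim 2, which tests agreement with raters; no planned analysis tests reproducibility directly

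*Combined protocol and SAP*

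**What the plan says.** Section 5 (Claims and intended performance) introduces the table this way: "The study aims to provide information that can be used to substantiate the claims listed in the table below". Claim 2 reads "Automated scoring algorithms that give reproducible scores time after time", and Aim 2 is the only aim entered against it.

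Aim 2 is described in four places, each time as agreement with human scoring:

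- Section 5, primary objective: "To assess the degree of agreement between the algorithm and manual scores for the digital Rey Osterrieth Complex Figure Test and Clock Drawing Test".
- Section 5, Hypothesis D: the algorithm score should correlate above .8 "to the score provided by manual scoring for the same drawings".
- Section 6.1, below Figure 1: "We will use the 100 sets of digital ROCFT and Clock Drawing Test drawings, randomly drawn from the full sample". Section 6.2 adds the meaning of the statistic: "Relative inter-rater agreement implies that the algorithm ranks examinees the same as expert raters".
- Section 7, Aim 2: a TOST on Fisher-transformed correlations compares algorithm-rater with rater-rater agreement, with bounds of r ± .1, six raters and 100 drawings. It adds that any correlation above .8 is enough for the sponsor's claim, without giving a claim number.

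On running the algorithm, section 6.2 says "Scoring algorithms for the ROCFT and the Clock Drawing Test are applied post-data collection". The number of runs per drawing is not stated.

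The only planned analysis of repeat performance is the test-retest comparison in section 7, Hypothesis B (group C for digital, group D for paper). It belongs to Aim 1, and section 7 opens by saying that the tests are scored by two raters.

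**The concern.** Agreement with raters and reproducibility are different properties. A fully repeatable algorithm can rank drawings differently from the raters and fail Aim 2. An algorithm with appreciable run-to-run noise can still correlate above .8 with the raters and pass. A correlation is also unchanged when a constant is added to every score, so a uniform shift between two runs would not show in it.

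If the table is followed as written, a favourable Aim 2 result will be cited for a property that Aim 2 did not measure directly. That property matters to the product: sections 2.2 and 3 present the tool as a means of comparing one person's performance across assessments, and a score that moved on rescoring would appear as change.

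**Working it through.** **1. The plan's own figure.** Section 7 states at least 80% power for the Aim 2 TOST. It comes from a simulation in a technical note whose inputs are not in the documents, so it cannot be reproduced. An illustrative simulation used 100 drawings, six raters, one common quality factor, one-sided alpha .05 and 1,000 studies per setting. When the algorithm behaved like another rater, the TOST passed in 99.8% to 100% of studies for inter-rater correlations of .80 to .95. This is consistent with the stated figure but does not verify it. The present point does not depend on it.

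**2. What an algorithm-rater correlation implies about rescoring.** If random errors are independent, the attenuation inequality gives

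r(algorithm, rater)² ≤ reliability(algorithm) × reliability(rater),

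so reliability(algorithm) ≥ r² / reliability(rater). At r = .8, r² = .64:

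| Inter-rater reliability (assumed) | Minimum rescoring reliability |
|---|---|
| 1.00 | .64 / 1.00 = .64 |
| .95 | .64 / .95 = .67 |
| .90 | .64 / .90 = .71 |
| .85 | .64 / .85 = .75 |
| .80 | .64 / .80 = .80 |

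These bounds apply to the true correlation; sampling error in 100 drawings loosens them.

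For scale, two runs on the same drawing differ with standard deviation √(2(1 − reliability)) in score-SD units. That is √(2 × .36) = .85 SD at reliability .64 and √(2 × .20) = .63 SD at .80. Neither would ordinarily be called reproducible time after time.

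**3. Can a noisy algorithm pass Aim 2?** The same model was used, with all of the algorithm's unreliability set to random rescoring noise, so that r(algorithm, rater) = √(rescoring reliability × inter-rater r). For example, √(.80 × .90) = .849. The table gives the share of simulated studies that met both the TOST (unpaired) and r > .8:

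| Inter-rater r (assumed) | Rescoring reliability .75 | .80 | .90 |
|---|---|---|---|
| .85 | 50% | 83% | 100% |
| .90 | 59% | 94% | 100% |
| .95 | 24% | 75% | 100% |

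**4. Does another analysis fill the gap?** Hypothesis B correlates scores of two separate drawings made weeks apart, from tests scored by human raters. No repeat run of the algorithm, repeatability statistic or criterion appears under Aims 1 to 4.

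**The case against.** The best defence is that Aim 2 is not empty as support for Claim 2. Section 6.2 describes its statistic as inter-rater reliability, and reliability between scorers is one accepted sense of reproducibility. Random scoring error lowers the correlation with raters, so a badly unstable algorithm would tend to fail Hypothesis D. The table promises information that can be used for the claims and does not say that Aim 2 is the only evidence. Whether fixed software returns the same score for the same file is ordinarily a software-verification matter, and section 2.1 places the product under a quality system with design control. Section 2.3 makes integration of the algorithms conditional on high agreement with manual scores, which Aim 2 does test.

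Most of this stands, and it limits the point. It does not remove it. The claim's wording is about repetition over time, the aim entered against it measures agreement at one comparison, and the plan cites no verification result for the claim. Whether such a result exists cannot be judged from these documents.

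Three stronger readings are tempting, and the documents support none of them:

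- *Each drawing is scored exactly once by the algorithm.* The plan is silent on the number of runs. The random draw from the full sample could even include both drawings of one person; no analysis pairs them.
- *The study yields no evidence on reproducibility.* The bound in step 2 of the working is evidence, though indirect and weak.
- *The group C retest would settle the matter.* It mixes scoring error with practice, real change and natural variation in drawing. A perfectly repeatable algorithm could show a modest retest correlation.

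**Conclusion.** The point holds as a mismatch between a claim and the analysis assigned to it. Aim 2 does not directly test reproducibility of the automated scores, no other planned analysis does, and a pass on Aim 2 does not by itself substantiate Claim 2.

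The indirect support is a minimum rescoring reliability of .64 at r = .8 with error-free raters, rising to .80 if inter-rater reliability is .80. The pass rates in step 3 rest on a one-factor model, on noise that is purely random, and on an assumed inter-rater range of .85 to .95. They show that passing is possible without high repeatability; they do not suggest that this algorithm is noisy. If the algorithm is deterministic, which the documents do not say, the direct check will be trivial to pass, and that check is then what the claim should cite.

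No hypothesis, sample size or participant procedure is affected.

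**What to change.** Do one of the following.

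1. **Reword Claim 2** to what Aim 2 tests: algorithm scores agree with manual scoring about as well as raters agree with each other. The cost is a narrower claim.
2. **Keep Claim 2 and add a direct check to Aim 2.** Run the final algorithm a second time on the same stored drawings, set identical scores as the criterion, and map Claim 2 to that result. The cost is one batch run and a few lines in section 7 and the claims table.

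Optionally, report the algorithm-scored phase 1 to phase 2 correlation in group C (n = 50) with a 95% CI, beside the manually scored value for the same drawings. Label it as test-retest reliability of the algorithm-scored test, including practice and real change, and not as proof of scoring reproducibility. Precision would be moderate. For an assumed r of .7, tanh(atanh(.7) ± 1.96/√47) = tanh(.867 ± .286), or .52 to .82. The drawings are already planned, so this needs no extra participants or visits.

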**Risks and adverse device effects:**

The following risks and anticipated adverse device effects to be assessed:

- Privacy breach
- Participant fatigue
- Data loss

**6 CLINICAL INVESTIGATION DESIGN**

**6.1 General**

The study has a randomized, counterbalanced design and consists of two phases (see figure 1). We sample participants according to the sampling plan outlined below, to ensure representativeness of the sample. We will oversample by 20% to account for dropout or incomplete data (the *n*'s below represent the desired cell counts, after dropout).

**Figure 1. Schematic overview of study design.**

Title: Clinical Investigation Plan		Author: [name]		Company Restricted	
DocID: ICBE-2-28674	Version: 2.0	Date: 2019-02-18	Status: Approved	Page: 21 of 35	
IRBMANAGER PILOT – QI PROJECT					

Group	A	B	C	D	E
n	100	100	50	50	100-150
Phase 1 tests	Digital	Paper-pencil	Digital	Paper-pencil	Digital
Phase 2 tests	Paper-pencil	Digital	Digital	Paper-pencil	

All participants of Group A-D in phase 1 will be invited to participate in two assessments that will take place with a time interval of four-five weeks between the two phases to minimize retest effects. Participants will be randomly assigned with minimization for demographic variables (to make sure that the groups do not differ in terms of gender, age, education level, and ethnicity) to one of the following groups:

- Group A ( $n=100$ ) completes digital tests in phase 1 and paper-pencil tests in phase 2,
- Group B ( $n=100$ ) completes paper-pencil tests in phase 1 and digital tests in phase 2,
- Group C ( $n=50$ ) completes digital tests in both phases,
- Group D ( $n=50$ ) completes paper-pencil tests in both phases,
- Group E ( $n=100-150$ ) only completes digital tests in one phase (50% of group E will be enrolled in phase 1 and the other 50% of group E will be enrolled in phase 2).

The data of group A and B are used to compare score distributions within-subjects

The data from groups A-D (phase 1) are used to compare score distributions between-subjects (aim 1).

The data of group C and D are used to assess and compare test-retest reliability (aim 1) and assess reliable change indices (aim 3).

The data of group A (phase 1), group C (phase 1) and group E are used to estimate regression based norms for the digital tests (aim 3), as well as to estimate factor loadings for the structural equation model (aim 4).

The data of group A (phase 1), group B (phase 1), group C (phase 1) and group D (phase 1) are used to compare construct validity (aim 1).

Participants will be randomized with minimization for demographic variables (gender, age, education level, ethnicity).

The purpose of adding the 100-150 participants in Group E is to increase the sample size of participants who completed the digital tests for the first time for the norm data to 250-300.

We will use the 100 sets of digital ROCFT and Clock Drawing Test drawings, randomly drawn from the full sample, to establish agreement between scoring algorithms and manual scoring by well-trained raters (aim 2).

Title: Clinical Investigation Plan		Author: [name]		Company Restricted	
DocID: ICBE-2-28674	Version: 2.0	Date: 2019-02-18	Status: Approved	Page: 22 of 35	
IRBMANAGER PILOT – QI PROJECT					

### 6.2 Investigational device(s) and comparator(s)

The investigational devices are the ISC product and the ISC product equivalent. The comparators are the paper-pencil tests included in the study.

Manual scores of the digital ROCFT and Clock Drawing Tests will be compared to the algorithm scores. Scoring algorithms for the ROCFT and the Clock Drawing Test are applied post-data collection. The scores estimated by the algorithms will be compared with manual scoring by a sample of well-trained raters (n = 6; aim 2). The algorithms have been developed by Philips Research and after positive comparison to the manual scores will be part of future releases of the ISC product. By comparing the manual and algorithm scoring, we can investigate the agreement between the two for the tests on the platform. This will be done by computing the relative inter-rater agreement (also known as inter-rater reliability) between the algorithm and expert raters. Relative inter-rater agreement implies that the algorithm ranks examinees the same as expert raters (n = 6).

### 6.3 Subjects

We have specified a Sampling plan that ensures representativeness for the US population in Appendix A. The sampling plan establishes initial normative reference ranges, provides psychometric evaluation of retest reliability, and provides a direct validation of digital scores relative to paper-and-pencil scores. Furthermore, this protocol establishes that older adults coming from a variety of backgrounds consistent with the general population of the United States can adequately follow the test administration rules with minimal proctoring, understand how to interact with the iPad to successfully enter his/her response to items, and a sufficient behavioral sample can be collected to establish reference ranges.

#### Inclusion criteria for subject selection

- Examinee’s primary language (language most often spoken) must be English.
- If examinee has vision impairment or hearing loss, must be corrected to normal.
- Must have normal fine and gross motor ability
- Must have use of fingers, hands, and arms to be able to use a pencil to write symbols.  
Must be able to understand subtest instructions and participate fully in testing

#### Exclusion criteria for subject selection

- Evidence of current cognitive impairment
- Disruptive behavior or insufficient compliance with testing to ensure a valid assessment.
- Examinee must not be currently admitted to a hospital, assisted living, nursing home or a psychiatric facility.
- Examinee must not be diagnosed with a neurological disorder or disease (e.g., Parkinson’s, brain tumor, stroke, TBI, epilepsy [if # seizures ≤ 2 and not receiving ongoing treatment for seizures, and not currently seeking medical evaluation or attention related to seizures, examinee can be accepted], encephalitis, dementia, language disorder (expressive or mixed receptive/expressive excluded; articulation disorder is ok), learning disorder
- Must not have been unconscious related to traumatic brain injury or “medical condition” > 20 minutes (however, e.g., heat stroke, medication induced are ok) or any head-injury resulting in an overnight hospital stay
- Any history of a medical event requiring resuscitation in which examinee was non-responsive for > 15 minutes.
- Must not have current or recent functional change (ability to carry out usual duties at work, in school, IADLs [driving, shopping, managing money], etc.) due to cognitive change.
- Examinee must not be receiving chemotherapy treatment, or have received chemotherapy treatment in the past 2 months.
- Examinee must not have a history of ECT or radiation to the CNS.
- Examinee must not be (currently or in the past) diagnosed with a psychotic disorder, or currently diagnosed with a mood disorder (however, Major Depressive Disorder in remission or with no

Title: Clinical Investigation Plan		Author: [name]		Company Restricted	
DocID: ICBE-2-28674	Version: 2.0	Date: 2019-02-18	Status: Approved	Page: 23 of 35	
IRBMANAGER PILOT – QI PROJECT					

- current episode, and Dysthymic and Adjustment Disorders, are acceptable) or an anxiety disorder with symptoms significant enough to interfere with optimal test performance.
- Autoimmune disorder (e.g., LUPUS, Multiple Sclerosis)
  - Examinee must not be currently diagnosed with substance abuse or dependence, or have carried any substance abuse or dependence diagnosis in the past year (> 1 year in remission diagnoses are ok). Long term alcohol abusers are excluded as well (e.g., abused substance for more than 10 years)
  - Any history of Autism Spectrum Disorder or Intellectual Disability.
  - The examinee must not be currently taking medication that might impact test performance (e.g., anti-convulsants, antipsychotics, benzodiazepines, psychostimulants, opioids, tricyclic antidepressants, some norepinephrine reuptake inhibitors). Most antihypertensive medications and statins are acceptable.
  - If previously diagnosed with any physical condition or illness that might depress test performance, illness must not interfere with normal cognitive functioning at work, school, ADLs, etc. Diabetes, hypothyroidism, and hypertension are acceptable if controlled.
  - Exclude primarily nonverbal or uncommunicative. Must not have a diagnosis of aphasia.
  - Examinees should not have received neuropsychological testing although previous MMSE testing is allowed if more than 6 months prior
  - Examinee must not be seeking medical diagnostic procedures for cognitive difficulties from a medical professional.
  - Non-valid health insurance in USA.

**Criteria and procedures for subject withdrawal or discontinuation**

Subjects will be enrolled when the inclusion criteria and exclusion criteria are met and when the subject has signed the informed consent form.

Subjects can leave the study at any time for any reason if they wish to do so without any consequences.

If one of the following criteria is fulfilled, the participation of a subject to the study is terminated:

- Subject indicates that he wishes to leave the study
- Subject is not able to use the iPad Pro (test data will not be destroyed but flagged as invalid)
- Subject does not meet inclusion/exclusion criteria anymore
- The investigator can decide to withdraw a subject from the study for medical reasons.

These subjects need to be replaced according to the sampling plan if test data of a subject are destroyed or test data are not complete due to study termination.

The point of enrolment is the time at which, following recruitment, a subject signs and dates the informed consent form. The first subject is expected to be enrolled in March 15 2019. The Clinical Investigation is expected to take 6 months.

The duration of each assessment is 90 minutes.

In this clinical investigation, the company that will recruit the participants will account for an expected dropout rate of 20%.

**6.4 Procedures**

**Specimen Banking (saving human fluid or tissue for future research)**

Not applicable—this is a human study without specimen banking.

**Clinical procedures**

Participants included in group A-D will be invited for an assessment on two different time points (phases). Both assessments will take approximately 1.5 hours. After signing an informed consent, participants will receive either all digital or all paper-pencil cognitive tests in phase 1 and either all digital or all paper-pencil cognitive tests in phase 2, depending on group assignment. See figure 1 for

Title: Clinical Investigation Plan		Author: [name]		Company Restricted
DocID: ICBE-2-28674	Version: 2.0	Date: 2019-02-18	Status: Approved	Page: 24 of 35
IRBMANAGER PILOT – QI PROJECT				

an overview of the study design. Participants included in group E of the study (see figure 1) will only receive one assessment (all digital cognitive tests). 50% of group E will be enrolled in phase 1 and the other 50% of group E will be enrolled in phase 2.

This assessment will take approximately 1.5 hours. All participants will be asked to complete a MoCA screener. The study will be concluded when each cell of the design (group A-E) meets its required sample size with participants that meet the inclusion criteria and completed the tests specified for their group.

